3.1 OVERALL TRIAL DESIGN AND PLAN

This is a Phase I open label, non-randomized bio-distribution trial to be conducted in one specialized center. The trial is divided in 2 Parts as described below in [Figure 3.1:1](#) and will be conducted in a staggered approach.

Part 1 – Dosimetry and feasibility assessment – up to 5 patients

Part 2 – Assessment of tumor uptake – up to 35 patients

[figure not shown]

Recommended exp. dose is the BI 754111 dose recommended for the expansion phase of trial 1381-0002.

Figure 3.1: 1 Overall design

- **Part 1** is intended to assess the dosimetry of $[^{89}\text{Zr}]\text{Zr-BI 754111}$, to optimize the imaging time window and the feasibility of $[^{89}\text{Zr}]\text{Zr-BI 754111}$ PET to assess tumor distribution and uptake of BI 754111. The BI 754111 dose administered in this Part will be the dose recommended for the expansion phase of trial 1381-0002. The whole body biodistribution of $[^{89}\text{Zr}]\text{Zr-BI 754111}$ will be assessed and optimal tumor uptake parameters will be developed. See [Figure 3.1: 2](#).

Proprietary confidential information © 2020 Boehringer Ingelheim International GmbH or one or more of its affiliated companies

[figure not shown]
PD= Progression of Disease Bx=Tumor Biopsy

Figure 3.1: 2 Part 1: dosimetry and feasibility assessment

- Part 2 will be initiated following a positive SMC decision after review of all available data from Part 1 in order to assess whether a blockade of $[^{89}\text{Zr}]\text{Zr}$ -BI 754111 has been demonstrated. Patients will be tested for tumor LAG-3 expression at screening. During cycle 1, all patients will undergo baseline PET assessments. During cycle 2 (on-treatment PET assessment), at least 2 doses levels of BI 754111 treatment will be explored in patients tested positive for tumor LAG-3 expression. At least 2 patients should be included per dose cohort. See [Figure 3.1: 3](#).

Up to five patients tested negative for LAG-3 expression will be included in Part 2. These patients will not be part of dose exploration but will be offered treatment with BI 754111 at the dose recommended for the expansion phase of trial 1381-0002. Hence, they will not undergo the on-treatment PET/CT assessment procedures.

After cycle 2, all patients will be treated at the recommended dose.

PD= Progression of Disease Bx=tumor biopsy PET/CT post $[^{89}\text{Zr}]\text{Zr}$ -BI 754111: 2 before CTP 3.0, 3 after CTP 3.0

Figure 3.1: 3 Part 2: assessment of tumor uptake

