3.2 DISCUSSION OF TRIAL DESIGN, INCLUDING THE CHOICE OF CONTROL GROUP(S)

Part 1 will assess the feasibility of the methods. The patients included in Part 1 will have a $[^{89}\text{Zr}]\text{Zr-BI 754111}$ infusion for a baseline PET assessment (prior to first BI 754111 treatment) at Cycle1 and another $[^{89}\text{Zr}]\text{Zr-BI 754111}$ infusion for on-treatment PET assessment (following first BI 754111 treatment) at Cycle2. The baseline PET assessment will include a dosimetry to investigate the tracer ($[^{89}\text{Zr}]\text{Zr-BI 754111}$) dose. During the on-treatment PET assessment, the patients will be administered the dose of BI 754111 recommended for the expansion phase of trial 1381-0002. This dose of BI 754111 treatment will be tested first to evaluate whether a blockade of the $[^{89}\text{Zr}]\text{Zr-BI 754111}$ is possible.

It is estimated that up to 5 patients will be included in Part 1.

The data obtained from these patients will be analysed and reviewed on a regular basis by the SMC. During the SMC reviews, the mass dose of $[^{89}\text{Zr}]\text{Zr-BI 754111}$ might be adapted as needed *based on all imaging data available*. Part 2 will commence based on SMC decision after review of all available data from Part 1.

Part 2 will assess the tumor uptake of $[^{89}\text{Zr}]\text{Zr-BI 754111}$. The patients will be prospectively tested for LAG-3 tumor expression.

The patient tested positive for LAG-3 tumor expression will be included in different dose-cohorts, each cohort exploring one dose of BI 754111 treatment during cycle 2. It is planned to explore at least 2 doses of BI 754111 treatment in this study. At least 2 patients with LAG-3 expressing tumor are needed in each dose cohort in order to assess the degree of blockade of $[^{89}\text{Zr}]\text{Zr-BI 754111}$ uptake upon a certain BI 754111 dose.

A cohort of maximum 5 patients tested negative for LAG-3 expression will be included in Part 2. These patients will undergo the baseline PET assessment for $[^{89}\text{Zr}]\text{Zr-BI 754111}$ tumor uptake but they will not be considered for dose exploration and will not proceed for the on-treatment PET assessment.

For each patient in Part 2, *the cold dose BI 754091 necessary to optimize $[^{89}\text{Zr}]\text{Zr-BI 754111}$* , the dose of BI 754111 treatment to be applied at cycle 2 and the imaging timepoints will be confirmed by the SMC with reference to the data available.

Up to 35 patients might need to be included in Part 2.

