5.6 OTHER ASSESSMENTS

5.6.1 FDG-PET/CT procedure

A standard static diagnostic FDG-PET will be performed during screening for the assessment of tumor viability and necrosis. This procedure will be performed in accordance with European Association of Nuclear Medicine (EANM) FDG-PET/CT procedures guidelines for tumor imaging ([R18-1536](#)).

5.6.2 $[^{89}\text{Zr}]\text{Zr-BI 754111}$ PET scan procedure

All PET scans will be performed on a PET/CT scanner (e.g. █████ Ingenuity TF). All patients will undergo whole body PET scans at various time points, e.g. $t = 72$ and $t = 144$ hours post-injection. The PET scans will be preceded by a 30 mAs low-dose CT, used for attenuation correction and anatomical localization of the PET-signal. Following CT, a total body PET scan will be acquired. PET scans consist of 10-12 bed positions, depending on the length of the patient, of various time lengths, usually 5 minutes each. Total acquisition time per scan, including low dose CT will be around 60 minutes.

PET data will be normalized and corrected for randoms, tissue attenuation, decay, scatter and dead time. PET-CT data will be reconstructed with TF-OSEM, resulting in a transaxial spatial resolution of ~ 7 mm in the centre of the field of view. Regions of interest (ROIs) will be defined using the CT images which are co-registered to the PET-CT data. ROIs around the organs which accumulate ^{89}Zr (e.g. liver, lung and other metastatic lesions) will be drawn manually directly on the PET images. All tissue concentrations will be related to the blood concentration (venous samples). The radioactivity concentrations in all regions for all imaging time points will be recorded digitally in a spreadsheet.

Quantitative accuracy of ^{89}Zr -PET scans was previously confirmed in █████ center using phantom studies and comparisons between PET-derived and biopsy tumor radioactivity concentrations ([R18-1538](#), [R18-1539](#)).

A blood sample (~ 6 mL) will be drawn *at four early time points post injection of $[^{89}\text{Zr}]\text{Zr-BI 754111}$ (after CTP 3.0) and at each $[^{89}\text{Zr}]\text{Zr-BI 754111}$ PET scan* to determine ^{89}Zr -kinetics based on measurements of radioactivity. See [Blood Sample Flow Chart](#) for time schedule. The detailed procedures of $[^{89}\text{Zr}]\text{Zr-BI 754111}$ PET/CT scanning will be described in the lab manual at the site.

Analysis of PET data:

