7.2 NULL AND ALTERNATIVE HYPOTHESES

It is not planned to test any statistical hypotheses in a confirmatory sense. All statistical analyses are exploratory even if they use confirmatory methods. Confidence intervals (CI) will be computed and will be interpreted in terms of the exploratory character of the study, i.e. confidence intervals are considered as interval estimates for effects.

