7.3 PLANNED ANALYSES

All individual data will be listed. Adherence to the protocol will be checked. Important protocol violations (IPVs) will be identified no later than in the Report Planning Meeting and provided in the trial statistical analysis plan (TSAP).

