7.4.1 Primary analysis of the primary endpoint(s)

The primary endpoint is defined as:

Mean relative change ($\Delta\text{SUV}_{\text{peak}}$) of the standardized uptake values (SUV_{peak}) from baseline (Cycle1 / C1) to on-treatment (Cycle2 / C2) PET assessments in all evaluable, metabolic active lesions.

Two PET imaging time points (PET assessments) will be considered for the calculation (2 time points for CTP v1/v2; 3 time points CTP v3/not applicable); the time point leading to the maximum effect (max. reduction from baseline) will be reported.

Calculation:

The primary endpoint is derived for each patient as follows:

- Calculate the relative change from baseline for each selected lesion at each time point (e.g. 96h, 144h):
$$100 * (\text{SUV}_{\text{peak,lesion,timepoint,C2}} - \text{SUV}_{\text{peak,lesion,timepoint,C1}}) / \text{SUV}_{\text{peak,lesion,timepoint,C1}}$$
- Calculate the mean over all evaluable lesions (at each time point)
- Select the lower mean, i.e. choose the time point with maximum average effect/reduction in tumor uptake from baseline ($= \Delta\text{SUV}_{\text{peak}}$)

The minimum mean $\Delta\text{SUV}_{\text{peak}}$ will be summarized per cohort (dose group of BI 754111 in Cycle2) as: N / Mean / SD / Min / Median / Max.

A similar analysis of minimum mean $\Delta\text{SUV}_{\text{peak}}$ will be presented for each patient as: N / Mean / SD / Min / Median / Max.

Tumor uptake at baseline:

The mean tumor uptake at baseline will be summarized per cohort (blocking dose of BI 754111 in Cycle2) separately for each imaging time point (96h, 144h) as the mean $\text{SUV}_{\text{peak,C1}}$ over all selected lesions as: N / Mean / SD / Min / Median / Max.

A similar analysis of mean tumor uptake (SUV_{peak}) at baseline (Cycle1) will be presented for each patient as: N / Mean / SD / Min / Median / Max.

Impact of CTP amendments:

As per CTP v3, the assessment of the primary endpoint was changed from 2 to 3 PET scans (imaging time points) to assess tumor uptake. The changes are not considered to impact on the primary endpoint; the reported effect is assumed to be fully captured in the time window. No patients were actually imaged as per CTP v3.

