7.4.2 Sensitivity analysis, subgroup analysis, exploratory analysis of the primary endpoint(s)

No sensitivity or further exploratory analyses of the primary endpoint will be performed.

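### The primary analysis keeps each patient's larger fall in uptake across two scan times, with no visible summary of the change at either time

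*SAP*

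**What the plan says.** The endpoint in Protocol 2.1.2 is SUVs at baseline and after the BI 754111 dose; it has no rule for choosing a scan time. SAP 7.4.1 turns this into one number per patient. It computes the percentage change in SUVpeak for each lesion at each of two scan times, averages over lesions at each time, and then instructs: "Select the lower mean, i.e. choose the time point with maximum average effect/reduction in tumor uptake from baseline". That minimum is summarised per cohort, and a similar summary is given per patient.

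Baseline uptake is handled differently: SAP 7.4.1 summarises it "separately for each imaging time point (96h, 144h". The visible text has no matching summary for the change or for Cycle 2 SUVpeak. SAP 7.4.2 adds: "No sensitivity or further exploratory analyses of the primary endpoint will be performed".

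Protocol 7.2 says: "Confidence intervals (CI) will be computed and will be interpreted in terms of the exploratory character of the study". It states no level, and the SAP's visible summary set contains no intervals. Protocol 7.3 says: "All individual data will be listed".

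**The concern.** The scan time is chosen separately for each patient, from that patient's own outcome, and in the direction of the expected effect. The cohort mean of the chosen values therefore lies, on average, below the mean change at either scan time and below the average of the two. A cohort can also mix scan times, so its mean need not describe any one of them.

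The main objective is uptake at baseline and how it changes on treatment, and Protocol 3.2 speaks of the degree of blockade at a given dose. A reader who takes the cohort mean as the change at one scan time, or as the average over both, reads more blockade than the data show there. Nothing visible tells that reader how much comes from the selection.

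**Working it through.** **Inputs.** From SAP 7.4.1: two scan times are used (no patient was imaged under the three-scan schedule), selection is within patient, and the lower mean is kept. From Protocol 3.1: "At least 2 patients should be included per dose cohort"; this gives the smallest cohort size below. Sizes 3 and 5 are illustrations. Neither document gives an SD, CV, correlation or expected change for SUVpeak. There is thus no planned figure to reproduce, and every size below rests on assumed noise.

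**Step 1: direction (no assumptions).** Let A and B be a patient's mean changes at the two scan times. Since min(A,B) ≤ A and min(A,B) ≤ B, E[min(A,B)] ≤ min(E[A], E[B]) at any sample size. Where every patient has both scans, the cohort mean of the minima cannot exceed the lower time-point mean. It equals it only if the same scan time is lower (or tied) in all patients. If some patients have one usable scan, this cohort-level inequality is no longer exact.

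**Step 2: size under normality.** Let D = A − B have SD s, which includes measurement noise and any real patient differences in timing. Then min(A,B) = (A + B)/2 − |D|/2.

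- Equal true changes: shift = −s/√(2π) = −0.399 s.
- True changes differing by d: shift below the larger true fall = d/2 − E|D|/2, where E|D| = s√(2/π)·exp(−d²/2s²) + d[1 − 2Φ(−d/s)].
- Example, d = 10 and s = 20: E|D| = 14.08 + 3.83 = 17.91, so the shift is 5 − 8.96 = −3.96.

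| d (points) | s = 5 | s = 10 | s = 20 | s = 30 |
|---|---|---|---|---|
| 0 | −2.0 | −4.0 | −8.0 | −12.0 |
| 10 | 0.0 | −0.8 | −4.0 | −7.6 |
| 20 | 0.0 | −0.1 | −1.7 | −4.5 |

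**Step 3: adding the noisy baseline.** The change is a ratio, so noise in the Cycle 1 denominator pushes every version upward, towards less blockade. With lognormal noise independent between cycles and a true Cycle 2/Cycle 1 ratio R, the expected change at one scan time is 100 × [R(1 + CV²) − 1]. At CV 15% this is +2.25 for R = 1, and 100 × (0.7 × 1.0225 − 1) = −28.4 for R = 0.7. The minimum was simulated. Middle case: CV 15%, correlation 0.5 between scans of one cycle, 3 lesions.

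| True changes (%) | Mean of the minimum | Mean at each scan time |
|---|---|---|
| 0 / 0 | −2.8 | +2.3 / +2.3 |
| −30 / −30 | −31.9 | −28.4 / −28.4 |
| −30 / −25 | −30.1 | −28.4 / −23.3 |
| −30 / −20 | −29.1 | −28.4 / −18.2 |

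Cross-check of the first row, taking the correlation on the log scale: s² = 2 × 1.0225² × (1.0225² − 1.0225)/3 = 0.01604, so s = 12.66 points. The shift is 0.399 × 12.66 = 5.05, and 2.25 − 5.05 = −2.80.

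Across 36 scenarios with no true change (CV 10–30%, correlation 0–0.8, 1–5 lesions):

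- The minimum lies below the single-time value in all 36, by 1.6 to 25.2 points.
- Against the truth of 0, the minimum is negative in 32 (down to −16.1) and positive in 4 (up to +3.6).
- The single-time value is always positive (+0.9 to +9.1).
- The minimum is nearer the truth in 18 of 36; one near-tie can fall either way between simulation runs.

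With correlation 0.95 in the middle case and no true change, the shift is only −1.6.

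**Step 4: mixing of scan times.** If p is the chance that the first scan time is selected, a cohort of n mixes times with probability 1 − pⁿ − (1 − p)ⁿ. In the middle case p is 0.50, 0.713 or 0.861.

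| True changes (%) | n = 2 | n = 3 | n = 5 |
|---|---|---|---|
| Equal | 50% | 75% | 94% |
| −30 / −25 | 41% | 61% | 81% |
| −30 / −20 | 24% | 36% | 53% |

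**The case against.** The SAP does not hide the rule: it calls the statistic the maximum reduction and the minimum mean. It also assumes that the scan window captures the whole effect. For someone who wants the maximum reduction, the minimum can do better than a single scan time: in the middle case, at −30/−25 and −30/−20, it is nearer to −30 than the better scan time is. Values at a fixed scan time carry ratio bias too. The trial is descriptive, has no test and was stopped early, and the documents do not show that any dose or Part 2 decision used this statistic. Individual data are to be listed, so with small cohorts the changes may be rebuilt by hand. Sections of the SAP are redacted, including the space between 7.5.2 and 7.7, and could hold a table by scan time.

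All of this stands, and it limits how large and how consequential the problem is. It does not remove the shift against either scan time. Nor does a listing replace a planned summary of the only primary endpoint. The redactions mean the gap is in the visible text only. The missing intervals are a separate, secondary matter, but Protocol 7.2 does promise them.

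**Conclusion.** The concern holds and should be fixed. Relative to the change at either scan time, the cohort mean of the minimum is shifted towards more blockade on average, by algebra alone, and the shift does not shrink with more patients. Its size cannot be taken from the documents. Under the normal model with s of 5 to 30 points it is 2 to 12 points if the true changes are equal, and at or near zero if one scan time dominates and s is small. Relative to the true change, the net error is usually but not always an overstatement, because the ratio bias runs the other way. This is a reporting gap in a descriptive analysis. It concerns how the estimate is read and has no bearing on type I error.

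**What to change.** In SAP 7.4.1:

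- Keep the minimum. Beside it, summarise per cohort the relative change and Cycle 2 SUVpeak at each nominal scan time, with N at each, in the layout already planned for baseline uptake.
- Report which scan time was selected for each patient.
- State that the minimum is the maximum observed reduction and is not an unbiased estimate of blockade at any scan time. Note that the percentage changes by scan time carry ratio bias as well.
- Add the interval estimates promised in Protocol 7.2 and state their level.
- If a redacted section already has the summary by scan time, a cross-reference from 7.4.1 is enough.

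No single fixed scan time is asked for. Protocol 5.6.2 says "All patients will undergo whole body PET scans at various time points", and Protocol 3.2 says that for each Part 2 patient "the imaging timepoints will be confirmed by the SMC with reference to the data available".

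The cost is SAP wording and a few table rows, with no new data. The added figures will on average show less blockade than the minimum: about 5 points less in the middle case with no true change (+2.3 against −2.8), but only 0.7 less at the better scan time when the true changes are −30/−20 (−28.4 against −29.1). The documents mention 72, 96 and 144 hours, so some rows may have few patients and wide intervals.

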7.4.2 Sensitivity analysis, subgroup analysis, exploratory analysis of the primary endpoint(s)

No sensitivity or further exploratory analyses of the primary endpoint will be performed.

7.5 SECONDARY ENDPOINT(S)

7.5.1 Key secondary endpoint(s)

This section is not applicable as no key secondary endpoint has been specified in the protocol.

Primary analysis of the key secondary endpoint(s)

[figure not shown]
This section is not applicable as no key secondary endpoint has been specified in the protocol.

[figure not shown]
Sensitivity analysis, subgroup analysis, exploratory analysis of the key secondary endpoint(s)

This section is not applicable as no key secondary endpoint has been specified in the protocol.

7.5.2 (Other) Secondary endpoint(s)

This section is not applicable as no secondary endpoint has been specified in the protocol.

7.7 EXTENT OF EXPOSURE

The total number of cycles initiated of BI 754111 / ezabenlimab will be summarized descriptively. This analysis will be based on all patients in the TS who received at least one cycle of nominal combination treatment of BI 754111 (600 mg) and ezabenlimab (240 mg).

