ipilimumab, for example, has resulted in significant improvement in ORR, compared to checkpoint inhibitor monotherapy in patients with NSCLC and melanoma ([R16-5545](#), [R15-3696](#), [R16-5544](#)). Unfortunately, the improved efficacy of combined nivolumab and ipilimumab was associated with a significant increase in the rate and severity of AEs. Grade 3 and 4 AE rates of 53% to 55% were reported with the full-dose combination of nivolumab and ipilimumab in patients with melanoma ([R15-3696](#), [R16-5544](#)) and 33% to 37% with reduced dose and dosing frequency of the ipilimumab component in NSCLC compared to approximately 10% for nivolumab monotherapy in these populations ([R15-3696](#), [R16-5544](#)).

Treatment with BI 754111 and BI 754091 is anticipated to be associated with a similar pattern of AEs. Immune-related AE management guidance will be provided in the trial documentation. Infusion-related reactions have been reported with checkpoint-inhibitor treatments. These reactions occur infrequently and are typically managed based on symptoms using treatments ranging from histamine antagonists in mild cases to administration of epinephrine when symptoms of anaphylaxis are detected. Detailed irAE management guidelines are presented in [Appendix 10.2](#).

Preliminary efficacy analyses indicate that there are 6 patients with Partial response (PR) and 20 patients with disease stabilization on BI 754091 monotherapy in the 1381-0001. The PRs were reported in 2 patients with triple negative breast cancer, 1 patient with fallopian tube cancer, 1 patient with renal cancer, 1 patient with stomach cancer *and one patient with endometrial cancer*. All of these PRs occurred in patients receiving the 240 mg q3w dose of BI 754091.

BI 754091 has also been administered in combination with BI 754111 (monoclonal IgG4pro antibody targeting the human LAG-3) to 86 patients with advanced/metastatic solid tumors in trial 1381.2. Fifty five of these patients have been treated with 240 mg BI 754091 in combination with increasing doses of BI 754111 (Q3W). In the dose expansion portion of the

Proprietary confidential information © 2020 Boehringer Ingelheim International GmbH or one or more of its affiliated companies

study, 31 patients have been treated with 240 mg BI 754091 in combination with 600 mg BI 754111 Q3W.

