4.1.4 Drug assignment and administration of doses for each patient

The tracer dose (approximately 4mg in 20mL) of [⁸⁹Zr]Zr-BI 754111 will be injected intravenously via a pump in 10 min with flushing (10 mL physiologic saline). The mass dose might be adapted as per SMC decision. The injection will take place at the department of [REDACTED] Each patient will be administered [⁸⁹Zr]Zr-BI 754111 up to 2 times during the trial, once at Cycle1 no later than Day8 and at Cycle2 after the administration of BI 754091/BI 754111 treatment, if applicable (all patients in Part 1 and only patients tested positive for tumor LAG-3 expression in Part 2).

BI 754091 will be administered via intravenous infusion at the dose of 240mg. The first administration of BI 754091 treatment will take place at Cycle1 Day1 for each patient.

BI 754111 will be administered via intravenous infusion at the recommended expansion dose per trial 1381-0002. The first administration of BI 754111 treatment will take place at Cycle2 Day1 for each patient.

In Part 2, patients tested positive for tumor LAG-3 expression will be administered a lower or a higher dose of BI 754111 treatment at Cycle2 only. The dose allocated at these patients in Cycle2 will be confirmed by the SMC.

At Cycle2 and onwards, BI 754091 and BI 754111 treatment will be administered concomitantly.

For the preparation and administration of BI 754091 and BI 754111, please refer to the instruction provided in the ISF.

For each compound, the different timepoints of administration and the different doses are summarized in the table below.

Table 4.1.4: 1 Administration of doses per study part

Treatment Cycle	Study Part	Day	Dose to be administered
Cycle1 Baseline assessment	Part 1 and Part 2	C1 Day1	BI 754091 treatment: 240mg
		No later than day8	[⁸⁹ Zr]Zr-BI 754111: 4mg or adapted mass dose
Cycle2 On-treatment assessment	Part 1	C2 Day1	BI 754091 treatment: 240mg
			BI 754111 treatment: recommended exp. dose
	Part 2	C2 Day1	[⁸⁹ Zr]Zr-BI 754111: 4mg or adapted mass dose
			BI 754091 treatment: 240mg
			BI 754111 treatment: allocated dose per SMC decision
			[⁸⁹ Zr]Zr-BI 754111: 4mg or adapted mass dose
Cycle 3 and further cycles	Part 1 and Part 2	Cx Day1	BI 754091 treatment: 240mg
			BI 754111 treatment: recommended exp. dose

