4.3 TREATMENT COMPLIANCE

BI 754111 and BI 754091 will be administered by i.v. infusion at the sites by the Investigator and/or trained site personnel, and dosing will be recorded in the eCRF. Therefore, actual dosing is expected to precisely follow the prescribed drug regimen. Missed or interrupted doses will be recorded in the eCRF with the associated reasons. The method of collecting dosing information assures that total exposure can be calculated programmatically taking into account any missing doses.

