6.3 SUBJECT SETS ANALYSED

Screened Set (SCS)

[figure not shown]
This patient set includes all patients who have signed the informed consent. The screened set will be used for patient disposition tables.

Treated Set (TS)

This patient set includes all patients who were documented to have received at least one dose of [⁸⁹Zr]Zr-BI 754111, BI 754111, or ezabenlimab. The TS will be used for all safety and efficacy analyses including the primary analysis.

Pharmacokinetic Analysis Set (PKS)

All evaluable patients in the TS which provide at least one evaluable observation for at least one PK endpoint and no PK relevant protocol violation. PKS is used for pharmacokinetical analysis.

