7.8 SAFETY ANALYSIS

All safety analyses will be performed on the treated set (TS). Treated patients will be analyzed according to their initial treatment.

Analyses will be performed as defined in Section 7.3.3 of the CTP. In general, safety analyses will be descriptive in nature and will be based on BI standards. No hypothesis testing is planned.

Safety data recorded during the Residual Effect Period (REP) of 30 days will be considered as on-treatment.

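### SAP 7.7 summarises exposure only in patients who received a 600 mg combination cycle, so it leaves out the shortest-treated patients in the safety population

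*SAP*

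**What the plan says.** **Exposure.** SAP 7.7 contains one analysis: "The total number of cycles initiated of BI 754111 / ezabenlimab will be summarized descriptively". It covers patients in the treated set (TS) "who received at least one cycle of nominal combination treatment of BI 754111 (600 mg) and ezabenlimab (240 mg" (closing bracket omitted).

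**Safety.** SAP 7.8 states: "All safety analyses will be performed on the treated set (TS" (closing bracket omitted). SAP 6.3 defines that set as patients who "received at least one dose of [⁸⁹Zr]Zr-BI 754111, BI 754111, or ezabenlimab", so a single dose of any of the three products is enough.

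**Dosing.** Cycle 1 is ezabenlimab (BI 754091) plus the tracer, and BI 754111 treatment starts on Day 1 of Cycle 2 (Protocol 4.1.2.2). For Part 1, "The BI 754111 dose administered in this Part will be the dose recommended for the expansion phase of trial 1381-0002". The protocol and SAP show this dose as 600 mg: in that trial's expansion, "31 patients have been treated with 240 mg BI 754091 in combination with 600 mg BI 754111 Q3W" (Protocol 1.4), and SAP 6.1 names 600 mg with 240 mg as the combination. LAG-3 negative patients in Part 2 are offered the same dose (Protocol 3.1). LAG-3 positive patients in Part 2 "will be administered a lower or a higher dose of BI 754111 treatment at Cycle2 only" (Protocol 4.1.4). From Cycle 3 everyone moves to the recommended dose (Protocol 4.1.2.2).

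**Early stopping.** SAP 6.1 foresees patients who stop before Cycle 3. It keeps them in the safety analysis and labels them by the doses they received in Cycles 1 and 2. It also groups the reported data by the Cycle 2 blocking dose.

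**The concern.** An exposure table is normally read as the background to the adverse event tables: how much drug the patients at risk received. Here the two have different populations, and the difference is not random. Entry to the 7.7 summary requires a patient to stay on treatment until a 600 mg combination cycle. The patients removed are those with the fewest cycles, so the mean and minimum number of cycles can only stay the same or rise.

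The required cycle may also differ by cohort. For a patient given 600 mg at Cycle 2 the condition is met at Cycle 2. For a patient given another dose it is met at Cycle 3 at the earliest. Two patients with the same number of cycles could then be treated differently.

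Cohorts can be very small, since Protocol 3.1 asks for at least 2 patients per dose. One omitted patient could halve a cohort. No readable section of the SAP summarises the exposure of the omitted patients elsewhere, and SAP 7.3 declares treatment compliance not applicable.

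**Working it through.** The plan gives no figure to reproduce. The check has two steps: apply the 7.7 condition to each possible treatment course, then show how the displayed mean could move under stated assumptions.

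**Step 1: who is included.** The inputs are the dosing rules in Protocol 3.1, 4.1.2.2 and 4.1.4, the TS definition in SAP 6.3, and the condition in SAP 7.7. The condition can be read in two ways. The plain reading takes any cycle with 600 mg plus 240 mg. The Cycle 3 reading takes nominal in the sense of SAP 6.1, which ties nominal medication to the start of Cycle 3.

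| Cycle 2 dose of BI 754111 | Last cycle started | In TS (safety) | In 7.7, plain reading | In 7.7, Cycle 3 reading |
|---|---|---|---|---|
| Not reached | 1 | yes | no | no |
| 600 mg | 2 | yes | **yes** | no |
| Other dose | 2 | yes | **no** | no |
| Either | 3 or later | yes | yes | yes |

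Cycle 1 stoppers, and other-dose patients who stop after Cycle 2, are out under both readings. The cohorts differ in one row only, last cycle 2, and only under the plain reading.

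**Step 2: possible effect on the mean.** These inputs are assumed; none is in the documents. Count combination cycles (BI 754111 at any dose with ezabenlimab). Suppose every patient starts Cycle 2, a share q stops after it with 1 combination cycle, and the rest average m combination cycles.

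- Mean over all these patients: q × 1 + (1 − q) × m
- Mean displayed where Cycle 2 stoppers are omitted: m

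| q | m | Mean, all patients | Mean displayed | Ratio |
|---|---|---|---|---|
| 0 | any | m | m | 1.00 |
| 0.1 | 4 | 0.1 + 3.6 = 3.7 | 4 | 1.08 |
| 0.1 | 6 | 0.1 + 5.4 = 5.5 | 6 | 1.09 |
| 0.3 | 4 | 0.3 + 2.8 = 3.1 | 4 | 1.29 |
| 0.3 | 6 | 0.3 + 4.2 = 4.5 | 6 | 1.33 |
| 0.5 | 4 | 0.5 + 2.0 = 2.5 | 4 | 1.60 |
| 0.5 | 6 | 0.5 + 3.0 = 3.5 | 6 | 1.71 |

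Under the plain reading, the 600 mg cohort would show the third column and an other-dose cohort the fourth, although their exposure is identical. Under the Cycle 3 reading, both would show the fourth. Patients who stop in Cycle 1 have zero combination cycles. They would lower the full-TS mean further and leave the displayed mean unchanged.

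**A four-patient example, also assumed.** Let total cycles started, counting Cycle 1, be 2, 3, 4 and 6. The mean over all four is (2 + 3 + 4 + 6)/4 = 3.75. Without the patient who stopped after Cycle 2 it is (3 + 4 + 6)/3 = 4.33. The ratio is 4.33/3.75 = 1.16, and the minimum rises from 2 to 3. One patient produces the whole difference.

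**The case against.** The strongest reply is that SAP 7.7 declares its population openly. Cycles among patients who received the intended combination are a legitimate description of those patients. The protocol's statistical section specifies no exposure analysis that 7.7 could contradict. Protocol 4.3 says that "total exposure can be calculated programmatically taking into account any missing doses", which describes what the data allow and does not promise a summary over the whole TS. This stands: no rule in the documents is broken, and the point concerns completeness.

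A reader might infer several stronger things that the documents do not support.

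- *That the plan certainly treats the cohorts unequally.* This holds on the plain wording, which names a dose and no cycle. SAP 6.1 uses nominal for the medication at Cycle 3. If 7.7 means that, early stoppers leave every cohort alike. The inequality goes, but the omission grows.
- *That the omitted patients would appear in adverse event tables with no exposure on record.* They would not. SAP 6.1 labels them by their actual doses, and Protocol 7.3 has all individual data listed. They are missing from one summary.
- *That adverse events and exposure will be compared side by side by Cycle 2 cohort.* SAP 7.7 sets no display by cohort; the grouping comes from the general statement in SAP 6.1. SAP 6.1 also labels on-treatment data by the Cycle 3 medication, and SAP 7.8.1 displays adverse events by the dose on the first day of treatment.
- *That exposure is overstated by some known percentage, or that the early stoppers stopped for toxicity.* The documents give neither the number of patients per Cycle 2 dose, nor the number who stopped before Cycle 3, nor their reasons.

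**Conclusion.** The point holds as a modest one about a descriptive table. The exposure population in SAP 7.7 is conditioned on a 600 mg combination cycle. It can therefore be smaller than the safety population, and it leaves out patients with the least treatment under either reading of the text. The direction is clear: the summary would tend to overstate exposure in the treated set. The size cannot be stated. It is nil if nobody stopped in Cycle 1 and no patient given another Cycle 2 dose stopped before Cycle 3 (under the Cycle 3 reading, if nobody stopped before Cycle 3). Under the assumptions above, the displayed mean is about 8% to 71% too high when 10% to 50% of those who started Cycle 2 stop after it. Whether the omission also differs between Cycle 2 doses depends on what nominal means, which the SAP should say. The primary endpoint is not affected.

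**What to change.** Replace the population in SAP 7.7 with wording such as:

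> Exposure is summarised for every patient in the TS, by BI 754111 dose at Cycle 2 and in total. The summary gives the number of ezabenlimab cycles started and the number of BI 754111 cycles started at any dose, counting a patient with none as zero. BI 754111 cycles started at 600 mg may be shown as a further row.

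Patients who never start Cycle 2 need a stated place in the table, either a row of their own or the total only. The optional 600 mg row keeps the description of the intended combination, so nothing in the present table is lost. Separate counts for the two drugs also settle whether Cycle 1, which contains no BI 754111 treatment dose, counts as a cycle. If the sponsor prefers to keep the restricted population as an additional display, 7.7 should define nominal and name the cycle from which it applies.

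The cost is one sentence and one table shell, using dosing data already recorded in the eCRF (Protocol 4.3). The mean number of cycles may come out slightly lower. The total exposure column then has the same denominator as the safety analysis.
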